9.3 VARIABLES

9.3.1 Exposures

Study Treatments

The treatment variables below are identified at the patient eye level and will be used to describe the treatment patterns throughout the analysis. These treatment variables will be analyzed throughout the entire study period. Each treatment type can only occur once per patient eye visit and will be identified at every distinct visit where the following codes are present. Treatment must contain both the Current Procedural Terminology (CPT) codes for intravitreal injection and the J-codes specifying the study treatment (Table 2).

Though not common, it is possible for multiple different treatment types to occur on the same day, in which case both treatments would be captured for analysis i.e., a patient could get a laser and an injection at the same visit.

Table 2. Study Treatment Definitions

Study Treatment Definitions		
Treatment	CPT Code	
		[REDACTED]
		[REDACTED], C9214, C9257, Q9977
		Eylea- J0178, C9291, Q2046
		Lucentis-J2778, C9233
		Beovu- J0179

BOEHRINGER INGELHEIM Group of Companies

NIS Protocol Template

Study number: 1484.0014

Page 16 of 30

Document number: <insert>

		Susvimo – C9093, J2779 Byooviz- Q5124 Vabysmo- J2777, C9097 Cimerli- C9097, Q5128
Corticosteroids	Intravitreal Injection – 67028	Ozurdex-J7312 Triamcinolone-J3300, J3301 Iluvien-J7313 Yutiq-J7314
Laser	Focal Grid Laser- 67210 Panretinal Photocoagulation- 67228	Not Applicable
C3 Inhibitor	[REDACTED]	J3490, C9399

[REDACTED] will also accept an incoming procedure medication that is associated to an [REDACTED]
[REDACTED]
[REDACTED]

9.3.2 **Outcomes**9.3.2.1 Primary outcomes

- [REDACTED]

This study will evaluate the disease progression over time. The main progression endpoints will be for the study eye, [REDACTED], changes in the GA lesion location, changes in the VA or changes in the size of the GA lesion. For the fellow eye the progression endpoints will also include the developing of GA.

*Please see Table 1, that includes the disease definitions (dry AMD, GA, and wAMD) based on ICD codes.

- **Position of GA lesion will be assessed over time.** The position of GA lesion will be defined using ICD 10 coding defined below. Any change in location status will be identified as progression of GA

Study Disease Definitions-lesion location		
	GA without Subfoveal Involvement	GA with Subfoveal Involvement
ICD 10	H35.3113, H35.3123, H35.3133, H35.3193,	H35.3114, H35.3124, H35.3134, H35.3194

BOEHRINGER INGELHEIM Group of Companies

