NIS Protocol Template

Study number: 1484.0014

Page 17 of 30

Document number: <insert>

- **Increase in the size of GA lesion will be assessed over time.** The size of GA lesion will be further defined following feasibility of data availability, with the basis of the lesion size defined using text field extracts. An example of text entries available for classification are defined below. Note that any analysis involving lesion size will need to be run on a subset population where these data are available/documentated;
Small: “Non-Central Geographic Atrophy, Small.”;
Medium: “Moderate Geographic Atrophy (Juxtafoveal)”;
Large: “1.5 DD Central Geographic Atrophy, Large.”, “Central Geographic Atrophy, Large.”, “4+ Geographic Atrophy.”
- **Progression of GA by Visual Acuity**

Change in visual acuity over time will be tracked from the incident date of GA, and assessed on a yearly basis in order to track the progression of GA over time. In this study, visual acuity will be defined as follows:

[REDACTED] receives VA data from Snellen charts in over 98% of cases, with some other types (ex. Jaeger, charts) in the remainder. There are no instances of ETDRS being received since all data are coming from private retina clinics. All VA entries are standardized and converted to LogMAR for reporting purposes. [REDACTED] standard output for VA is in the form of [REDACTED]

[REDACTED] will only compare VA results of a patient if vision is taken by the same measurement method; i.e., if a patient has their vision recorded using a DCC measurement at index diagnosis, for the remainder of the study, only DCC measurements will be accepted for comparison. This is done to ensure that any change in VA is due to actual change in the patients' vision, and not due to them taking a different vision test. Further, where DCC is not available for VA, any other measurements will be used, ensuring the same type of measurement will be used for the same eye to estimate the changes over time. The ranking order for measurement types is DCC ->NCC ->PH ->DSc ->NSc.

When capturing VA at different time points of interest, a buffer is allowed on either side of the date to increase the chances of each eye coming in for a visit. Should an eye have 2 readings inside the buffer window, the reading closest to the date of interest is taken. The buffers are proposed as follows:

- Index Diagnosis: +/- 30 days
- Follow up reading at Month 6, 12, or 18: +/- 30 days

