9.5 STUDY SIZE

During the development of the protocol and while running the projects viability, a feasibility was run on the database identifying both patients and eyes with Dry AMD, and specifically with GA. This analysis was run using only ICD 10 codes and with the use of exam notes. Actual population counts are subject to change based on the dataset available at first data run, but all analysis will be based on the assumption that population sizes are relative to these numbers.

GEOGRAPHIC ATROPHY (PERIOD >=2016) (ICD 10 + Exam Notes)

# of Patients	72,718
# of Eyes	113,408
Avg months of follow-up	22
# of Patients with visits after 3 years	20,503
# of Eyes with visits after 3 years	31,647

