9.7 DATA ANALYSIS

9.7.1 Main analysis

All analysis will be performed individually on the study population(s). All study results will be provided in tables, and key findings will be highlighted and summarized. The analyses will be conducted at both the patient and patient eye level, as appropriate.

Analysis for objective:

To describe the characteristics* of patients with GA in at least one eye.

To describe characteristics* of the study eye and the fellow eye, at index diagnosis (i.e., proportion of patients with GA in the fellow eye, [REDACTED]

All demographics, and clinical characteristics will be summarized at the index diagnosis date (first diagnosis of GA in the study eye).

Characteristics include demographics, comorbidities, comedications (patient level).

And at eye level; AMD, GA, eCNV, other ocular comorbidities, functional parameters i.e. VA. As well as treatments administered prior to or at index.

Summary will include descriptive statistics; continuous variables will consist of mean (SD) and median (IQR) while categorical variables will be described using frequency and proportion. Absolute numbers (n) of the variables (either yes or patients as appropriate) will be always included in the description of the results.

Analysis for objective:

To evaluate and characterize the progression of newly diagnosed patients with GA during a 5-year follow-up period. To describe patients' characteristics, study eye and the fellow eye characteristics, [REDACTED]

[REDACTED] or progression of the GA lesion in the study eye. To evaluate changes in VA, to evaluate changes in the lesion location, and lesion size (where available).

Patients with GA will be analyzed as an overall group. Subgroups will be also analyzed separately: only GA, GA and wAMD, GA and other comorbidities, and bilateral GA at baseline.

Ocular comorbidities will also be tracked longitudinally (yearly) from index date (GA diagnosis in the database) to better understand the disease journey.

Disease progression will be analyzed at both patient and each individual eye level.

Progression to dry AMD, to GA and to wAMD will be assessed independently using time to event analysis, and also the rate of progression that is seen in the study (2nd, 3rd, 4th, and 5th) years. Bilateral GA eyes at baseline will be evaluated for progression to wAMD

BOEHRINGER INGELHEIM Group of Companies**NIS Protocol Template****Study number: 1484.0014****Page 23 of 30****Document number: <insert>**

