For all time to event metrics, mean (SD), median and range will be summarized, while proportions will be summarized using N (%).

Kaplan Meier or Cox Hazard ratios may be applied when analyzing disease progression. Additionally, it will be determined how patients progress during the 1,2,3,4,5 years follow up according to the lesion location, and lesion size.

Analysis for objective:

To determine the occurrence of GA in the study eye during the study period (at the 12 (24, 36, 48, 60) month follow up period).

The calculation of the occurrence (new cases) of GA will be tracked against the overall number of patients included in the retinal specialist database (████████ database) in a time period (year) as the denominator initially.

The analysis to calculate the prevalent cases will include all patients with a GA diagnosis active in the database in the given time period in the numerator, and all patients included in the retinal specialist database (████████ database) will be used as the denominator initially.

Since, this analysis is referring to a population attending a retinal specialist during a given time period and therefore is not a general population-based estimates, in order to give a context to the data, the proportion of other common diagnosis in patients over 50 years or older attending the clinic in the same time period (e.g. diabetic macular edema, diabetic retinopathy, proliferative diabetic retinopathy, and wAMD) will be calculated. The denominator will be all patients attending to the retina specialist in the given time period using the age group category that is applicable in this study (50 years or older).

For the initial calculations, the look back period in 2015 will be used to discard patients with prevalence GA diagnosis in the subsequent years. prior diagnosis will be excluded and only new cases diagnosis in the time period will be considered in the numerator when calculating incidence.

The calculations will be conducted by calendar year, and absolute numbers (n) and correspondent percentage (%) will be provided. As a sub analysis, it will be evaluated if changes occurred after the third quarter of 2021, corresponding with the ██████████

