Subgroups will be compared against one another to identify any differences in populations leading to progression. The characteristics will be extracted at the time of assignation to the group i.e. patient do not [REDACTED] in year one is contributing with his characteristics extracted at year 1 to the group (no progressors), that patient [REDACTED] at year 5 is contributing with his characteristics extracted at year 5 to the progressor group.

Summary will include descriptive statistics; continuous variables will be described by absolute numbers, the mean (SD), median and range, while categorical variables will be described using frequency and proportion. For discrete demographics or clinical characteristics, chi-squared test of proportion will be done to assess meaningful difference (standardized mean difference SMD may be used as an alternative), while continuous variables will be analyzed using SMD. Following univariate analysis on each metric, a multivariate logistic regression model will be run including relevant metrics identified in the univariate analysis.

Additional information on the analysis is described below:**Patient Demographics (at index and follow up):**

BOEHRINGER INGELHEIM Group of Companies**NIS Protocol Template****Page 25 of 30****Study number: 1484.0014****Document number: <insert>**

N (%); Age, gender, region; Bilateral status, other eye related diagnosis in study and fellow eye; Distribution by months of follow up; Concomitant illnesses (diabetes, cataract, etc.); Lesion location and size (along with % capture rate)

Progression : Progression of GA over time; Fellow eye AMD status; [REDACTED] (study and fellow eye) Mean (median/IQR) time to conversion; Conversion to GA (fellow eye) Mean (median/IQR) time to conversion; Proportion of patients with wAMD and GA (N, %)

[figure not shown]
Treatment Characteristics (follow up): Number of visits over time; Number of treatments over time, Mean (median) time to study treatment; Type of treatment – Anti-VEGF, Laser, Combination, Mean (median) time on therapy

New cases occurrence and prevalent cases of GA (stratified by index year): N (%)

- Age, gender
- Distribution by months of follow up
- Calculation to the % of patients attending the retinal specialist over the same time period for other retinal conditions i.e. wAMD, DR, dry AMD or DME.

Visual Acuity Outcomes

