9.8 QUALITY CONTROL

The EMR information [REDACTED] receives is loaded into the input database unchanged. The incoming data are subject to quality control steps to ensure all the expected data are received and files are complete and readable. Changes in historic data are labeled as such and both original and modified values retained.

Input data are transformed into the operational database through a quality assurance process to ensure the validity of each data point. Metrics are tracked longitudinally to ensure logical consistency visits over visit, and are required to fall within specified limits (thresholds have been set using clinical insight from active retina specialists). Incidental Personal Health Information (PHI) contained in text fields are removed, information in text strings that contain multiple data elements are broken down into separate analyzable and standardized cells. [REDACTED]
[REDACTED]

All data shared with BI will be at an aggregated stage, and will be fully de-identified and HIPAA compliant

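### The lesion-location endpoint counts a change in either direction as progression and sets no at-risk group, so a recorded return from subfoveal to non-subfoveal GA is an event

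*Combined protocol and SAP*

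**What the plan says.** Section 9.3.2.1 (Primary outcomes) lists the main progression endpoints for the study eye. The unredacted part reads "changes in the GA lesion location, changes in the VA or changes in the size of the GA lesion". The location bullet takes its status from ICD-10 codes in a small table:

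- GA without subfoveal involvement: H35.3113, H35.3123, H35.3133, H35.3193.
- GA with subfoveal involvement: H35.3114, H35.3124, H35.3134, H35.3194.

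The event rule follows: "Any change in location status will be identified as progression of GA". The next bullet, on size, is worded differently: "Increase in the size of GA lesion will be assessed over time".

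Section 9.7.1 returns to location under the progression objective. It speaks only of evaluating changes in it and of describing progression at 1 to 5 years by location and size. It also says "Kaplan Meier or Cox Hazard ratios may be applied when analyzing disease progression".

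**The concern.** Progression implies movement one way, but the rule for location is symmetric. Two states allow two transitions, and the rule counts both. An eye that is already subfoveal at index cannot move forward on this measure, so its first location event, if it has one, must be a recorded reversal.

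Two things are at stake in the overall location result. The event count mixes forward changes with reversals. And because no denominator is tied to location at index, the rate may be taken over eyes that cannot progress on this scale. Two analysts could also report different results: one applies the sentence literally, the other assumes that only forward change was meant.

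**Working it through.** **Step 1: does any other section supply a direction or an at-risk set?**

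- Section 9.3.2.1, endpoint list: speaks of changes for location and size alike. The size bullet then narrows to an increase; the location bullet does not narrow.
- Section 9.7.1, progression objective and yearly description: no direction, and no restriction by location at index.
- Sections 4, 9.1.1 and 9.9: the restrictions on the progression population concern length of follow-up, valid VA readings and, possibly, two entries with progression data. None uses location.
- Sections 9.2.1 and 9.7.1: subfoveal versus extrafoveal is a subgroup split, not a statement of who is at risk of a location event.
- Section 9.8: general checks ("Metrics are tracked longitudinally to ensure logical consistency visits over visit"), with no stated rule for location codes.

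Nothing visible changes the literal reading.

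**Step 2: what the rule does to the rate.** The plan gives no rate or event count for this outcome, so there is no figure to reproduce. Three quantities are needed, and none is in the documents:

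- s = share of eyes coded 4 at index (assumed)
- f = proportion of eyes coded 3 at index with a 3-to-4 change (assumed)
- r = proportion of eyes coded 4 at index with a recorded 4-to-3 change (assumed)

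Counting the first change per eye, with all eyes in the denominator (also an assumption):

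- Reported rate R = (1 − s)f + s·r
- Forward rate among eyes that can progress = f
- Difference R − f = s(r − f)
- Share of events that are reversals = s·r / R

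For s = 50%, f = 20%, r = 5%: R = 0.5 × 0.20 + 0.5 × 0.05 = 0.125. The difference is 0.5 × (0.05 − 0.20) = −0.075, and the reversal share is 0.025 / 0.125 = 20%.

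Varying s, with f = 20% and r = 5%:

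| s | R | R − f | Reversal share |
|---|---|---|---|
| 25% | 16.25% | −3.75 points | 7.7% |
| 50% | 12.50% | −7.50 points | 20.0% |
| 75% | 8.75% | −11.25 points | 42.9% |

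**Step 3: two limiting cases.**

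- With r = 0, no reversal is ever recorded, yet R = (1 − s)f. At s = 50% and f = 20% that is 10% rather than 20%. The denominator problem does not depend on reversals.
- With r = f, R = f, so the rate is not shifted, yet a fraction s of the events are reversals.

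Over f = 10–40%, s = 25–75% and r = 1–10%, the reversal share runs from 0.8% (f = 40%, s = 25%, r = 1%) to 75% (f = 10%, s = 75%, r = 10%). That range shows how far the answer depends on unknown inputs. It is not an estimate.

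**The case against.** The strongest reply is that the plan already splits by location. Section 9.2.1 lists subfoveal versus extrafoveal as a subgroup for describing characteristics and progression, and section 9.7.1 repeats the grouping. If the groups are formed at index, every first location change in the extrafoveal group is forward and every one in the subfoveal group is a reversal, so the two can be told apart. This stands in part. A reader might infer that the results could never show how much of the counted progression is movement into the fovea; the documents do not support that. However, section 9.2.1 calls the subgroups proposed and open to modification, the time at which location is assigned is not clearly stated, and a subgroup does not change the event behind the overall rate. Section 9.7.1 also lists location under a heading covering index and follow-up, which would show the net shift between states but not individual transitions.

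A second reply concerns time-to-event analysis. A reader might infer that survival curves for location will take a reversal as the event. Section 9.7.1 assigns time-to-event analysis to progression to dry AMD, GA and wAMD and does not name location; Kaplan-Meier and Cox methods are only optional for progression in general. That consequence is possible, not planned.

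Third, reversals may be rare or removed by the section 9.8 checks, and the codes file named in section 15 is not available here. Both are fair cautions about impact. They do not alter the location sentence and its code table, which are complete and unredacted.

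**Conclusion.** The point holds as a fault in the event definition. As written, a recorded 4-to-3 change is progression, and no visible section restricts the outcome to eyes that can progress on it. It should be fixed, since location is one of the main progression endpoints.

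The impact on the results is unknown. The example (12.5% instead of 20%, with 20% of events being reversals) rests on assumed values of s, f and r and on an all-eyes denominator that the plan does not state. The reported rate falls below f whenever r is smaller than f, and by how much cannot be derived.

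A reader might also be tempted to apply an assumed reversal percentage to the 72,718 feasibility patients in section 9.5 to obtain a count of false progressions. The documents do not support that: progression analyses are limited to patients with follow-up, and the feasibility count drew on exam notes as well as codes.

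**What to change.** Replace the any-change rule with a directional one:

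- Event: the first change from an H35.31x3 code to an H35.31x4 code (x is the laterality digit).
- At risk: eyes coded x3 at index. Exclude eyes coded x4 at index from the denominator of this outcome only, and state how many there are.
- Report 4-to-3 changes separately, as coding inconsistencies.

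Optionally, a sensitivity analysis can require the x4 code to be confirmed at the next coded visit; it would lose eyes with no later coded visit.

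The cost is one sentence in section 9.3.2.1 and a code filter. No new data are needed, because location is already coded and is to be tabulated with its capture rate. The downside is that fewer eyes contribute to this outcome.

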9.3.3 Covariates

9.3.3.1 Demographic Characteristics: The demographic variables below are identified at the patient eye level and will be used to describe the demographic characteristics throughout the analysis. These demographic characteristics will be analyzed at the index diagnosis, unless specified elsewhere.

Age: will be calculated based on DOB from index diagnosis (incident visit).

Sex: identified at index diagnosis, or other visits if not specified.

Diagnosis year: Identified as the calendar year of the index diagnosis.

Months of History: will be defined as the time from index diagnosis to their last record in the database.

Incident Visit: The first visit in the database where one of the study diseases is identified, per eye. This may include Dry AMD, GA and/or wAMD. At incident visits all clinical characteristics, ocular comorbidities, etc. will be also captured.

Prevalent Visit: The first visit during a time period of interest where one of the study diseases is identified, per eye. This may include Dry AMD, GA and/or wAMD. This visit must not be the first diagnosis in the entire patient history. At prevalent visits changes in the clinical

BOEHRINGER INGELHEIM Group of Companies**NIS Protocol Template****Study number: 1484.0014****Page 19 of 30****Document number: <insert>**

characteristics, ocular comorbidities will be captured and described based on the first prevalent visit per calendar year.

9.3.3.2 Clinical Characteristics

Presence and Type of diabetes (T1DM/T2DM/Unspecified): Any ICD code identifying a specific type of diabetes will be used to identify a patient's diabetes status. The entire patient history prior to or on index diagnosis will be used in the identification process. Diabetes will also be identified based on the systemic drugs a patient is taking. Any type 2 drug will supersede a type 1 drugs. In the event that a patient has conflicting diabetes status using ICD codes and drugs, the ICD code will be used. A list of diabetic drugs can be found in the Appendix.

9.3.3.2.1 Ocular comorbidities defined using ICD codes (where available), listed in Appendix:

Ischemic optic neuropathy
 Glaucoma
 High myopia-pathologic myopia
 Uveitis
 Corneal transplant
 Incisional glaucoma surgery
 Retinal detachment
 Vitrectomy
 Multifocal choroiditis

Cataracts: **Cataracts presence** are defined using the ICD-9 and -10 codes to be listed in Appendix. Patient eyes will be identified as having cataracts at the index diagnosis.

Phakic Lens is an indication that the subject still has their natural lens intact, in the [REDACTED] database there will be no way to explicitly identify using "phakic" ICD codes. However, there will be several implicit ways in which phakic will be identified in this study:

-Free-text searches in exam section will be explored, for presence of terms such as 'clear lens', 'cataractous lens' or 'nuclear sclerosis'.

-Any ICD code identifying presence of cataracts or nuclear sclerosis (NS) information not identified on presence of an intra ocular lens will be used a definition for phakic.

Pseudophakic Lens will be defined using a combination of ICD Codes [ICD9] V43.1 or [ICD10] Z96.1[ICD9] 362.83, [ICD10] H35.31, CPT codes and free text searches.

Table 3: Other clinical conditions definitions-codes (ICD 9 and ICD 10)

[REDACTED]	[REDACTED]

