Population:	
Patients attending a retina specialist, contributing to the [REDACTED] Database. Patients will be identified in the database from January 1, 2015, to April 30, 2023.
 
From those, our study population will be patients ≥ 50 years with a GA diagnosis in at least one eye will be eligible for this study.
 
The study period was selected to be able to identify patients with GA using the ICD-10 codes introduced in that year. The period from January 2015 until October 1st, 2015 will be used to identify patients diagnosed with ICD-9 codes and further classify them as new cases or patients with an previous diagnoses.
		
Variables:	
A primary outcome variable is visual acuity (VA), reported using converted Early Treatment Diabetic Retinopathy Study (ETDRS) letters.
 
[REDACTED]
 
[REDACTED]
 
[REDACTED]
 
Demographic characteristics – including age, gender, patient history, visit history
 
Clinical Characteristics – including ocular comorbidities, lens status, systemic conditions
		
Data sources:	
The [REDACTED] database consists of de-identified Electronic Health Records from a geographically diverse panel of 360+ United States based private retinal specialists contributing data from 70+ practices. Over the datasets entire history, there have been about 2 million patients and about 13 million patient visits.
		

BOEHRINGER INGELHEIM Group of Companies

NIS Protocol Template

Page 9 of 30

Study number: 1484.0014

Document number: <insert>

Study size:	
All patients available in the database and meeting the study criteria will be included.
 
The [REDACTED] includes approximately 400,000 patient eyes diagnosed with dry AMD, and around 70,000 patients diagnosed with GA during the study period. After the initial feasibility analysis, it is expected, given the study criteria, that there will be around 100,000 eyes included. However, this number might change in the final analysis.
									

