9. RESEARCH METHODS

9.1 STUDY DESIGN

This is an observational cohort study based on existing data.

BOEHRINGER INGELHEIM Group of Companies**NIS Protocol Template****Study number: 1484.0014****Page 12 of 30****Document number: <insert>****9.1.1 Study population**

Study inclusion criteria: All patients ≥ 50 years, with a GA diagnosis in at least one eye, including in the [REDACTED] database identified during the study period (January 2015 to April 2023).

Exclusion criteria: Patients without the information of laterality will be excluded.

No other exclusion criteria are applied for the identification of the study population and description of the patients and eye at baseline.

Additional note:

For certain analysis the patient population will be restricted to those with at least 12, 24, 36, 48, or 60 months of history following diagnosis of GA. For the analysis requiring a VA reading, a restriction to those patients with valid VA readings at the index diagnosis and the respective follow-up times will be applied.

For analysis estimating the size of the GA population relative to other retinal diseases, the same timeframe requirements that the study population will be applied. In this population, any patient in the database will be eligible, and the diagnosis of DME, DR or other conditions may be used for subgroup comparisons.

Primary Disease Definitions

In the [REDACTED] Database, retinal and other diseases are identified using the International Classification of Diseases (ICD), Tenth Revision, Clinical Modification. ICD 10 codes were launched in the USA in October 2015, and are the only version of ICD codes with adequate descriptions of GA and dry AMD severity. As such, only ICD 10 codes will be analyzed in this study and the study period defined above is directly related to the launch of ICD 10 plus a small buffer allowing for physician familiarity.

These codes are entered by the physician at patient visit, with an associated laterality. This, along with the ICD 10 laterality is used in combination to confirm in which eye the disease is occurring. For this study, a patient eye will be considered to have the study disease so long as there is an accompanying ICD code. The primary study diseases to be analyzed are dry AMD, GA and wAMD, and will be identified using the ICD codes in Table 1 below.

Table 1. Study disease definitions-codes.

Study Disease Definitions			
	Dry AMD*	Dry AMD with GA*	wAMD*

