ICD 10	H35.311X, H35.312X, H35.313X, H35.319X	H35.3113, H35.3114, H35.3123, H35.3124, H35.3133, H35.3134, H35.3193, H35.3194	H35.321X, H35.322X, H35.323X, H35.329X
ICD 9 (2015 only)	362.51	N/A	362.52

*a comprehensive list of all AMD ICD codes is included in the Appendix

BOEHRINGER INGELHEIM Group of Companies**NIS Protocol Template****Study number: 1484.0014****Page 13 of 30****Document number: <insert>**

Patients could have simultaneously a diagnosis of wAMD and GA in the same eye. If both conditions are present, wAMD will be described as part of the comorbidities of the study or fellow eye. Patients could also have other ocular comorbidities affecting VA (section 9.3.3), those will be described and for the progression analysis will be analyzed separately.

For the follow-up analysis in the study eye or fellow eye, results will be described for all GA patients, patients with GA and wAMD, and patients with patients with GA only (without wAMD or other ocular comorbidities).

As the progression analysis tracking multiple different metrics across 2 eyes, it will be conducted at the patient level. Bilateral AMD disease is quite common (and will be identified), therefore the following methodology will be used to identify the 'Study' (primary) eye and the 'Fellow' (secondary) eye:

Study Eye – The first study eye in patient history identified with GA in the [REDACTED] database. GA is the only identifying disease in this case, and wAMD or dry AMD (without GA) in the study eye is not taken into account for study eye definition. If patients are bilaterally diagnosed, the study eye will be selected at random.

Fellow Eye – is defined as the other eye in a patient having their study eye diagnosed with GA. The fellow eye can have dry AMD, wAMD, GA or other retinal conditions. The fellow eye will be followed for progression purposes throughout the study.

Disease Status

Patient eyes will be identified at every visit throughout the study period to estimate the first time occurrence of GA and to estimate the proportion of patient with the disease over the years of the study period. Each visit will be classified as either an incident or a prevalent visit, defined below:

Incident visit – The first visit in patient eye history identified with GA in the [REDACTED] database. This timepoint also acts as each patients' index diagnosis. The incident visit may only occur once and contribute to one calendar year.

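### The pseudophakic lens definition lists ICD-10 H35.31, the stem of the study's own GA and dry AMD codes, and gives no rule for combining or matching the codes

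*Combined protocol and SAP*

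**What the plan says.** Lens status is a planned covariate. The Abstract, under Variables, lists "Clinical Characteristics – including ocular comorbidities, lens status, systemic conditions".

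Section 9.3.3.2.1 gives the rule for pseudophakic eyes: "Pseudophakic Lens will be defined using a combination of ICD Codes [ICD9] V43.1 or [ICD10] Z96.1[ICD9] 362.83, [ICD10] H35.31, CPT codes and free text searches". It does not say how the elements are joined or how the codes are matched.

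The same section finds phakic eyes by two routes. The first is exam text: "Free-text searches in exam section will be explored, for presence of terms such as 'clear lens', 'cataractous lens' or 'nuclear sclerosis". The second is by diagnosis code, and its rule begins: "Any ICD code identifying presence of cataracts or nuclear sclerosis (NS) information not identified on presence of an intra ocular lens will be used a". An eye that meets this rule counts as phakic. Cataract presence is a separate variable with its own codes.

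Table 1 in Section 9.1.1 gives the disease codes:
- GA: "H35.3113, H35.3114, H35.3123, H35.3124, H35.3133, H35.3134, H35.3193, H35.3194"
- dry AMD: "H35.311X, H35.312X, H35.313X, H35.319X"
- wAMD: "H35.321X, H35.322X, H35.323X, H35.329X"

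Under Primary Disease Definitions, Section 9.1.1 makes a code sufficient for disease status: "a patient eye will be considered to have the study disease so long as there is an accompanying ICD code".

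**The concern.** A code that the plan uses to identify dry AMD and GA appears in a rule meant to identify the state of the lens. Depending on how a programmer reads the sentence, the GA diagnosis that brings an eye into the study could also label it pseudophakic.

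Section 9.7.1 summarises clinical characteristics at index. It then compares characteristics between progression subgroups and carries the relevant ones into a logistic model. A pseudophakic flag that is the same for every GA eye would give a wrong row in the baseline table. It would also show no difference in the univariate step, so lens status would be passed over whatever its true relation to progression. Visual acuity is a primary outcome and Section 9.3.2.2 tracks cataract removal as a procedure, so a valid lens variable also helps a reader interpret visual acuity change.

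**Working it through.** The plan states no figure for lens status, so there is none to reproduce. The check compares code lists and then gives a scale.

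**Step 1: compare H35.31 with Table 1.**

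| Group | Entries | Begin with H35.31 | Equal H35.31 exactly |
|---|---|---|---|
| GA | 8 | 8 | 0 |
| Dry AMD | 4 | 4 | 0 |
| wAMD | 4 | 0 | 0 |

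**Step 2: apply each reading of the definition.**

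- *Any one element suffices, stem match.* Every ICD-coded GA eye is flagged, because the GA code itself meets the rule. Specificity in these eyes is 0. Fellow eyes with a dry AMD or GA code are flagged too; fellow eyes with only a wAMD code are not flagged by this route.
- *Any one element suffices, exact match.* No Table 1 entry is the bare stem, so H35.31 adds no eye coded under Table 1.
- *(V43.1 or Z96.1) and (362.83 or H35.31), stem match.* The second condition is always met in ICD-coded GA eyes. The code part of the flag reduces to V43.1 or Z96.1 and remains informative.
- *The same combination, exact match.* H35.31 again adds no eye. Requiring it would instead shut out eyes that have a lens code unless 362.83 is also present.

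In no case does H35.31 help to tell a pseudophakic eye from a phakic one.

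**Step 3: set this against the phakic rule.** Take the first reading. The exam-text route does not depend on H35.31, so a GA eye whose notes describe a cataractous lens would be phakic by text and pseudophakic by code. For the diagnosis-code route, the outcome depends on whether the pseudophakic flag counts as identifying an intraocular lens. If it does, this route closes for every ICD-coded GA eye. If it does not, a GA eye with a cataract code carries both labels. The plan does not say which. Section 9.3.3.2 gives a precedence rule for conflicting diabetes information but none for lens status.

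**Step 4: scale under the first reading.** Section 9.5 reports 113,408 GA eyes in 72,718 patients. The true pseudophakic share p is not in the documents; 30% to 70% is an assumption. Eyes wrongly flagged = N × (1 − p).

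| Assumed p | All GA eyes, N = 113,408 | One study eye per patient, N = 72,718 |
|---|---|---|
| 30% | 113,408 × 0.70 = 79,386 | 72,718 × 0.70 = 50,903 |
| 50% | 113,408 × 0.50 = 56,704 | 72,718 × 0.50 = 36,359 |
| 70% | 113,408 × 0.30 = 34,022 | 72,718 × 0.30 = 21,815 |

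Section 9.1.1 defines one study eye per patient, so the right-hand column applies to study-eye tables. Both counts come from ICD-10 codes plus exam notes. Eyes found from notes alone may carry no H35.31 code, so these are upper figures for each p.

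**The case against.** The strongest reply is that this is a slip in a code list. The printed pair does not match the plan's own coding: Table 1 pairs dry AMD with ICD-9 362.51, not 362.83. The two codes follow Z96.1 without a separator, just above a redacted table of ICD-9 and ICD-10 codes, and PDF conversion may have played a part. Annex 1 says that all variable definitions are in a Codes Appendix, which is not among the documents and may give the correct list and logic. This bears on how serious the point is. The sentence in 9.3.3.2.1 is still an operative definition that includes a disease stem, and it needs correcting whatever the appendix says.

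A reader might go further than the documents allow in four ways.
- *Every GA eye is pseudophakic as the plan is written.* This needs both single-element logic and stem matching. It is a natural reading of a code list, but the text says only that a combination is used.
- *Lens status carries no information.* Even on the worst reading, the exam-text phakic route and the separate cataract variable still vary. The result is contradictory flags, not the loss of all lens information.
- *An exact match would still mislabel fellow eyes with unstaged dry AMD.* Table 1 has no bare H35.31, and nothing shows that any eye carries it.
- *The visual acuity results are at risk.* The visible analysis text plans no split of visual acuity by lens status, and the visible subgroup list does not include it.

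**Conclusion.** The definition is wrong as written, with limited reach. It is certain that H35.31 is the stem of all eight GA codes and all four dry AMD families and is not a marker of lens status, and that the joining and matching rules are not stated. The consequence is conditional. With single-element logic and a stem match, all ICD-coded GA eyes are flagged; at an assumed true share of 30% to 70%, the remaining 70% to 30% are misclassified, all in one direction. With a combined rule or an exact match, H35.31 adds nothing in the eyes coded under Table 1.

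The variable affected is a descriptive baseline covariate that may reach the progressor comparison and its logistic model. No primary endpoint depends on it in the visible text. This is a code-list correction that should be made before the data run, not a threat to the main results.

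**What to change.** Before the data run:

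1. Remove H35.31 from the pseudophakic definition in 9.3.3.2.1. Remove ICD-9 362.83, or correct it if it stands for another intended code. Make the same change in the Codes Appendix if the codes appear there.
2. Define pseudophakic for each eye as any one of: V43.1 or Z96.1, a relevant CPT code, or lens free text, recorded on or before index.
3. Apply the phakic rule only to eyes that do not meet this definition, so that no eye carries both labels.
4. Check the other covariate code lists for overlap with Table 1.

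The cost is a short protocol edit and a check of the code lists. No new data are needed.
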